If ≥ 2 patients develop the same CTCAE grade 3 adverse event or 1 patient develops a CTCAE grade 4 adverse event, the study will be suspended until the DSMB reviews the events and makes a determination whether to continue. If a Grade 3 or worse event is clearly attributable to a non-treatment event and therefore not a suspected adverse reaction: [21CFR312.32(a)] the event will not be considered for the purposes of stopping.

Number of patients: up to 28 patients are planned for inclusion, 14 in each vision cohort

Diagnosis and main criteria for inclusion:

Inclusion Criteria

The following conditions must be met before a subject may be enrolled in the study.

- 1. Willing to give written informed consent, able to make the required study visits and follow study protocol instructions.
- 2. Willing to consent to gene mutation typing. Mutation typing will be restricted to typing for eye disease-related genes known to be involved in inherited retinal degenerations and related disorders. If typing results are already available for the subject, the previous results can be recorded and this requirement is waived.
- 3. Clinical diagnosis of RP confirmed by ERG.
- 4. BCVA 20/200 or worse and no worse than HM in cohort 1; and BCVA 20/40 or worse and no worse than 20/200 for the second cohort.
- 5. Male or female, age ≥ 18 yr.
- 6. Adequate organ function:
 - blood counts (hematocrit, Hgb, WBC, platelets and differential) within normal range, or if outside of normal range, not clinically significant as judged by the investigator
 - \circ liver function: alanine transaminase [ALT] and aspartate transaminase [AST] ≤ 2 times the upper limit of the normal range
 - \circ total bilirubin ≤ 1.5 times the upper limit of the normal range
 - \circ renal function: serum creatinine ≤ 1.25 times the upper limit of the normal range
- 7. Negative infectious disease screen (hepatitis B, C or HIV); and drugs of abuse (negative urine screen).
- 8. A female patient of childbearing potential (not surgically sterlized and less than one year postmenopausal) must have a negative pregnancy test (urine human chorionic gonadotropin) at entry (prior to injection) and must have used medically accepted contraception for at least one month prior to treatment. Women of childbearing potential and men must be advised to use a medically accepted method of contraception for at

NAME OF COMPANY: jCyte, Inc	SUMMARY TABLE	(For national Authority Use Only)
NAME OF FINISHED PRODUCT:	Volume:	
jCell	Page:	

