1.0 INTRODUCTION

1.1 Background

1.1.1 Retinitis Pigmentosa

Retinitis pigmentosa (RP) refers to a group of inherited diseases causing retinal degeneration. The cell-rich retina lines the back inside wall of the eye. It is responsible for capturing images from the environment. People with RP experience a gradual decline in their vision because photoreceptor cells (rods and cones) die. Forms of RP and related diseases include Usher syndrome, Leber's congenital amaurosis, rod-cone degeneration, Bardet-Biedl syndrome, and Refsum disease, among others.

In most forms of RP, rods are affected first. Because rods are concentrated in the outer portions of the retina and are triggered by dim light, their degeneration affects peripheral and night vision. When the more centrally located cones - responsible for color and sharp central vision - become involved, the loss is in color perception and central vision. Night blindness is one of the earliest and most frequent symptoms of RP.

RP is typically diagnosed in adolescents and young adults. The classic clinical sign of the disease is the presence of dark deposits in the retina. The main risk factor is a family history of retinitis pigmentosa. It is an uncommon condition affecting about 1 in 4,000 people or roughly 100,000 individuals in the US¹. Cases of RP are associated with a wide variety of known gene mutations, with new mutations still being discovered. The mutations can be inherited from one or both parents, or occur spontaneously; the pattern of inheritance can be autosomal recessive, autosomal dominant, X-linked or mitochondrial.

There is no effective treatment for RP; once photoreceptors are lost, they do not regenerate. The rate of deterioration of vision varies from person to person, with most people with RP legally blind by age 40. People with RP also often develop cataracts at an early age, or swelling of the retina (retinal edema). Numerous breakthroughs in the treatment of cataract and corneal disease have greatly decreased the incidence of blindness from these causes. In contrast, treatment of retinal and optic nerve disease is more limited, with these conditions now representing major causes of incurable visual loss and a significant unmet medical need.

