8.1.5 Ophthalmic AEs

Procedures will be performed at scheduled intervals to specifically assess eye AEs that may not be detected by usual AE reporting. Please refer to the study procedure manual for details of all ophthalmologic assessment procedures.

Slit lamp and fundus exam - The binocular slit-lamp examination provides a stereoscopic magnified view of the eye structures in detail, enabling anatomical diagnoses to be made for a variety of eye conditions. This assessment will include detection of anterior chamber cell or flare; acute cataract development or progression in phakic patients, or vitreous haze. Fundus exam allows for inspection of the retina, the cellular graft, and detection of retinal detachment.

B-scan – B-scan is a test that uses high-frequency sound waves to get measurements and produce detailed images of the eye. This test may provide information regarding the location of the injected cells and the size of the cell clusters at different time points during the study.

IOP - Intraocular pressure is measured with a tonometer as part of a comprehensive eye examination. Measured values of intraocular pressure are influenced by corneal thickness and rigidity

Spectral Domain Optical Coherence Tomography (OCT) - A clinical OCT machine will be used for data collection; the same machine should be used for any given patient at each time point. OCT tests, including assessment of the ellipsoid zone (EZ), will be analyzed to help define retinal anatomy, and will enable monitoring for ocular inflammation after treatment as manifest by cystoid macular edema or epiretinal membrane formation or progression.

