4. DETERMINATION OF SAMPLE SIZE

The sample size for this study was not based on any formal statistical considerations.

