8.1 Efficacy Variables

The response to jCell injection will be assessed based on the following:

- Best Corrected Visual Acuity (BCVA): BCVA will be measured with the electronic visual acuity testing algorithm (E-ETDRS). For each time point assessed, the total number of letter missed using E-ETDRS will be recorded for each eye and recorded on the Best Corrected Visual Acuity (BCVA) case report form.
- Electroretinogram (ERG): For each eye, A-wave Amplitude, B-wave Amplitude, Time from Flash Onset to A-wave Trough and Time from Flash Onset B-wave peak will be measured under the following conditions:
 - Dark adapted 0.01 ERG (rod response)
 - Dark adapted 3.0 ERG (rod-cone response)
 - Light adapted 3.0 ERG (single flash cone response)
 - Light adapted 3.0 flicker ERG

In addition, an overall assessment of Normal or Abnormal will be recorded for each condition. For those assessments of Abnormal, whether the assessment was Clinically Significant will also be reported. If Clinically Significant value is not reported in the follow-up visit, then the value will be imputed based on the value of previous visit, consistent with CRF completion guidelines. For example, if abnormal change from previous visit is "NO" then imputed value will be value from the previous visit.

• Optical Coherence Tomography (OCT): for assessment of OCT, the central subfield thickness reported on the Optical Coherence Tomography case report

jCyte, Inc	Statistical Analysis Plan
Protocol No. JC-01	08Nov2017

form will be used. Also information recorded at each visit as to whether Cystoid macular edema (CME) was present and if so, did it involve the foveal center will also be considered.

- Fluorescein Angiography: information regarding active leakage (Yes/No) and ischemia (Yes/No) will be collected for each eye for each Fluorescein Angiography performed.
- Autofluorescence: an overall assessment of Normal or Abnormal will be recorded for each eye for each fundus auto fluorescence imaging performed. For those assessments of Abnormal, whether the assessment was Clinically Significant will also be reported. If Clinically Significant value is not reported in the follow-up visit, then the value will be imputed based on the value of previous visit, consistent with CRF completion guidelines. For example, if abnormal change from previous visit is "NO" then imputed value will be value from the previous visit.

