9. METHODS OF EFFICACY ANALYSIS

Since this is an exploratory study, no formal hypothesis testing will be done. Descriptive statistics will be used to tabulate and summarize study outcomes. The baseline results of clinical examinations of the non-injected (non-study) eye serve as controls for the injected (study) eye. Results of clinical testing of the non-injected eye will also be described. Continuous variables will be summarized descriptively (sample size, mean, standard deviation and error, minimum and maximum). Discrete variables will be summarized by frequency or percentage. All efficacy analyses will be based on the ITT Population. All efficacy variables will be presented by cohort and dose level using summary statistics.

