10.7.6 Optical Coherence Tomography (OCT)

OCT results will be summarized in a table showing the counts and percentages of subjects whose eyes (both study eye and non-study eye) show cystoid macular edema present, and of those who do, how many cases involve the foveal center.

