		Baseline	Yes/No	Date9. (xx)	Time5.	Time5.					Abnormal CS	Yes/No	XXXXXXXXX
		Month6	Yes/No	Not Done:	Time5.	Time5.					Abnormal NCS	Yes/No	XXXXXXXXX
				reason									
		Month12											
Cohort 2 - 0.5×10^6 hRPC	XXXXXX	Screening	Yes/No	Date9. (xx)	Time5.	Time5.					Normal		
		Baseline	Yes/No	Date9. (xx)	Time5.	Time5.					Abnormal NCS	Yes/No	XXXXXXXXX
		Month6 Month12	Yes/No	Date9. (xx)	Time5.	Time5.					Abnormal CS	Yes/No	XXXXXXXXX

Note: CS=Clinically Significant, NCS=Not Clinically Significant. path\l program.sas date time

.

Programmer Note: If NO marked for testing, include reason in "ERG Date" column.

Programmer Note: Include Description of Abnormality and Clinically Significant information in "Result" column.

Programmer Note: Repeat columns for Dark Adapted 3.0 ERG (Rod Cone Response), Light Adapted 3.0 (Single Rod Cone Response), Light Adapted 3.0 Flicker ERG.

Programmer Note: 16.2.6.2.2 Repeat same for left Eye columns for Dark Adopted 0.01 ERG (rod response), Dark Adapted 3.0 ERG (Rod Cone Response), Light Adapted 3.0 (Single Rod Cone Response), Light Adapted 3.0 Flicker ERG.

			Assessment				
			Date (Study	Cystoid Macular Edema	IF CME Present, Involve	OD Central Subfield	OS Central Subfield
Treatment Group	Subject ID	Visit	Day)	(CME) Present?	Foveal Center?	Thickness (um)	Thickness (um)
Cohort 1 - 0.5 x 10 ⁶ hRPC	XXXXXX	Baseline	Date9. (xx)	Yes/No	Yes/No	XXX	XXX
		Day 28	Date9. (xx)	Yes/No	Yes/No	XXX	XXX
		Month 3	Date9. (xx)	Yes/No	Yes/No	XXX	XXX
		Month 6	Date9. (xx)	Yes/No	Yes/No	XXX	XXX
		Month 12 or Early	Date9. (xx)	Yes/No	Yes/No	XXX	XXX
		Termination					
Cohort 2 - 0.5 x 10 ⁶ hRPC	XXXXXX	Baseline	Date9. (xx)	Yes/No	Yes/No	XXX	XXX
		Day 28	Date9. (xx)	Yes/No	Yes/No	XXX	XXX
		Month 3	Date9. (xx)	Yes/No	Yes/No	XXX	XXX
		Month 6	Date9. (xx)	Yes/No	Yes/No	XXX	XXX
		Month 12 or Early	Date9. (xx)	Yes/No	Yes/No	XXX	XXX
		Termination	()				

path\l_program.sas date time

Programmer Note: If NO marked for testing, include reason in "Assessment Date" column.

Listing 16.2.6.4 Fluorescein Angiography

					OD (Right)				OS	OS (Left)		
			Assessment			Active		Other		Active		Other
Treatment Group	Subject ID	Visit	Date(Study Day)	Imaging Type	Start Time	Leakage?	Ischemia?	Observations	Start Time	Leakage?	Ischemia?	Observations
Cohort 1 - 0.5 x 10 ⁶ hRPC	XXXXXX	Baseline	Date9. (xx)	Field Imaging	Time5.	Yes/No	Yes/No	XXXXXX	Time5.	Yes/No	Yes/No	XXXXXX

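### The planned OCT tables count CME visit by visit with no new-onset row, so they cannot separate post-injection from pre-existing CME; the OCT listing as drawn also gives CME no eye

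*SAP*

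**What the plan says.** **Role of CME.** Protocol 8.1.5 says that OCT will "enable monitoring for ocular inflammation after treatment as manifest by cystoid macular edema", and names epiretinal membrane as the second sign. SAP 10.7.6 places the CME summary in the safety section.

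**Background edema.** Protocol 1.1.1 states: "People with RP also often develop cataracts at an early age, or swelling of the retina (retinal edema". Exclusion criterion 1 (Protocol 4.2) names only clinically significant macular edema.

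**Variable.** SAP 8.1 has "Also information recorded at each visit as to whether Cystoid macular edema (CME) was present and if so, did it involve the foveal center", and names no eye. In the same section BCVA, ERG, fluorescein angiography, autofluorescence and visual field are all described per eye.

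**Tables.** SAP 10.7.6 plans counts and percentages of "subjects whose eyes (both study eye and non-study eye) show cystoid macular edema present", and of foveal involvement among those with CME. The layout in Appendix C gives n/N (%) at baseline, Day 28 and Months 3, 6, 9 and 12 (or early termination). It has no change, shift, new-onset or resolved row. Table 14.3.4.12.2 repeats it for the non-study eye.

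**Listing.** The OCT layout in Appendix D has one CME column and one foveal-center column (its heading begins "IF CME Present, Involve"), neither labelled by eye. The two thickness columns beside them are labelled OD and OS.

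**Setting.** "Since this is an exploratory study, no formal hypothesis testing will be done" (SAP 9). Enrolment is "up to 28 patients are planned for inclusion, 14 in each vision cohort" (Protocol synopsis), and SAP 4 adds: "The sample size for this study was not based on any formal statistical considerations".

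**The concern.** The study's primary objective is safety, and CME is the only OCT result that the SAP tabulates: thickness appears only in the listing, and no OCT table covers epiretinal membrane. The useful safety question is whether treated eyes develop CME after the injection. A count of eyes with CME at each visit does not answer it where some eyes have CME at entry. One eye that resolves and another that develops CME cancel out, and the table reads as no change.

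The second issue is which eye. The two tables need a CME status for each eye, while the listing shows one status per visit. Nothing in the SAP says how a single Yes/No would become two eye-specific counts.

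**Working it through.** There is no plan figure for CME to reproduce: the documents give no CME rate, power or margin. The enrolment arithmetic agrees with itself: 4 + 4 + 3 + 3 = 14 per cohort, and 2 × 14 = 28. The dose columns of the tables therefore hold 3 or 4 subjects each.

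**A. What two cross-sectional counts say about new cases**

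Take n subjects assessed at both visits, one eye each. Let b have CME at baseline, f at a later visit, and let x be the new cases. Then:

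- resolved cases = b − f + x, which cannot be negative, so x ≥ f − b;
- x cannot exceed f, nor the n − b eyes free of CME at baseline.

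Hence max(0, f − b) ≤ x ≤ min(f, n − b). The counts below are illustrative.

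| Group | n | b | f | Fewest new | Most new |
|---|---|---|---|---|---|
| Dose column | 3 | 1 | 1 | 0 | min(1, 2) = 1 |
| Dose column | 4 | 1 | 1 | 0 | min(1, 3) = 1 |
| Dose column | 4 | 2 | 2 | 0 | min(2, 2) = 2 |
| One cohort, columns added | 14 | 3 | 3 | 0 | min(3, 11) = 3 |
| All subjects | 28 | 6 | 6 | 0 | min(6, 22) = 6 |
| Any group, none at baseline | n | 0 | f | f | f |

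So 2/4 and 2/4 fits no new case at all, or two new cases with two resolved. The last row shows the limit of the point: with no CME at baseline, every later case is new and the table is exact. A new-onset row reduces each range to a single number.

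**B. The eye**

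| Place in the SAP | CME | Thickness |
|---|---|---|
| 8.1 text | no eye stated | no eye stated |
| OCT listing, Appendix D | one column, no eye | OD and OS |
| 10.7.6, Tables 14.3.4.12.1/.2 | study and non-study eye | not tabulated |

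Suppose only a flag without an eye were held, and k subjects were positive. Each would be positive in the study eye only, the fellow eye only, or both, which gives (k + 1)(k + 2)/2 possible pairs of study-eye and fellow-eye counts: 3 for k = 1, 6 for k = 2, 10 for k = 3 and 15 for k = 4. The study-eye count could be anything from 0 to k. One subject wrongly placed moves a dose column by 1/4 = 25 or 1/3 = 33 percentage points. Part B is conditional on the CRF; part A is not.

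**The case against.** **The eye may well be captured.** A reader might infer that CME is recorded once per visit without an eye, so that the two tables cannot be derived. The documents do not support this. The CRF is not among them. SAP 8.1 is equally silent about the eye for thickness, which the listing then gives for OD and OS, so silence there proves nothing. SAP 10.7.6, the table index and the programmer note for Table 14.3.4.12.2 all presuppose eye-level CME, and Appendix A lets listings gain variables during programming. An under-drawn listing explains the conflict as well as a missing field does. This objection stands.

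**Other outputs carry part of the signal.** A reader might also infer that the OCT inflammation signal is uninterpretable. That is too strong. The subject listing shows CME by visit, so a change from No to Yes can be read off in groups of 3 or 4. Macula examination, fluorescein angiography and thickness are available by eye. New CME could also enter the adverse event tables. This stands in part. As drawn, the listing cannot say which eye changed, would miss a second eye becoming affected, and has no Month 9 row. Month 6 angiography is done only if CME is seen on OCT. The adverse event listing has no eye column.

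**No between-eye CME contrast is planned.** A study-minus-fellow difference forced to zero is therefore not a consequence to claim; the SAP plans such a difference only for BCVA.

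**The study is small and descriptive, and clinically significant edema is excluded.** True, and this limits background CME without removing it. A descriptive safety table should still count the event of interest.

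**Conclusion.** The point holds for the tables whatever the CRF contains. Tables 14.3.4.12.1 and 14.3.4.12.2 show how many eyes have CME at each visit and cannot separate CME arising after injection from CME present at entry. The size depends on how much CME there is at baseline, which the documents do not give. Equal counts of 2/4 leave 0 to 2 new cases open and equal counts of 6/28 leave 0 to 6; with none at baseline nothing is lost. These ranges assume the same subjects at both visits. Summaries use observed data only (SAP 8.3), so changing denominators would add to the uncertainty.

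The listing conflict is real as a matter of text: one CME field and one foveal-center field without an eye, against two eye-specific tables. Whether it is more than a drafting gap cannot be decided from the documents. Neither part affects the sample size or any test, since none is planned. This is a nearly free improvement to a safety summary.

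**What to change.** 1. In Tables 14.3.4.12.1 and 14.3.4.12.2 add, for each eye and post-baseline visit, a row for CME new since baseline among eyes without CME at baseline, and a row for CME resolved among eyes that had it. Add the equivalent row for new foveal-center involvement. Use as denominator the eyes assessed at both visits. The cost is a few table rows derived from planned data.
2. Confirm against the CRF that CME and foveal involvement are captured for OD and OS. If they are, state the eye in SAP 8.1 and split the two listing columns. That is a text and layout change only.
3. Only if the CRF lacks the eye, obtain it by data query from the stored OCT scan or its report. This is the one step with real cost, and it assumes that those records were kept.
4. While editing the listing, reconcile Month 9: Protocol Table 2 and the SAP table layout include OCT at that visit, while Protocol 7.5.12 and the OCT listing do not.

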8.2 Baseline Values

Unless otherwise noted, baseline is defined as the value obtained at baseline visit. If the baseline value is missing, the baseline value will be the last non-missing value recorded prior to the first dose of study drug.

8.3 Handling of Dropouts or Missing Data

No imputations will be made for missing values. Summaries will be based on observed data only.

8.4 Interim Analysis and Data Monitoring

There are no planned interim analyses for this study.

8.5 Examination of Subgroups

There are no planned subgroup analyses for this study.

8.6 Multiple Comparison/Multiplicity

No adjustments for multiplicity will be made in this study.

8.7 Multicenter Studies

Analyses to compare differences in response by center or any treatment by center interactions are not planned.

9. METHODS OF EFFICACY ANALYSIS

Since this is an exploratory study, no formal hypothesis testing will be done. Descriptive statistics will be used to tabulate and summarize study outcomes. The baseline results of clinical examinations of the non-injected (non-study) eye serve as controls for the injected (study) eye. Results of clinical testing of the non-injected eye will also be described. Continuous variables will be summarized descriptively (sample size, mean, standard deviation and error, minimum and maximum). Discrete variables will be summarized by frequency or percentage. All efficacy analyses will be based on the ITT Population. All efficacy variables will be presented by cohort and dose level using summary statistics.

9.1 Best Corrected Visual Acuity (BCVA)

For BCVA, summary statistics of the total number of letters correct (Letters correct=100-letters missed) will be generated at each time point for each cohort. Separate tables will be created for the Study Eye and the Non-Study Eye. In addition, change from baseline will also be summarized for each post baseline time point. For individual subjects who have number scores, the same formula for letters correct will be used to calculate each time point (letters correct = 100-letters missed). For subjects who do not have a number score e.g. counting fingers (CF), hand motions (HM) or no light perception)NLP), letters missed will be considered to be 100 and letters correct will therefore be zero. summarized (i) proportion of treated eyes with ≥ 5 , ≥ 10 and ≥ 15 letter

jCyte, Inc	Statistical Analysis Plan
Protocol No. JC-01	08Nov2017

improvements at any timepoint in the study same for untreated eyes at month 3,6,9 and 12 or Early Termination.

In addition, change in BCVA from baseline will be summarized for each dose level combining cohorts 1 and 2 at month 3,6,9 and 12 or early termination. Difference of mean change in BCVA between treated eye and non-treated eye from baseline will be summarized at month 3,6,9 and 12 or early termination. Furthermore, proportion of \geq 5, \geq 10 and \geq 15 letter improvements will be summarized for each dose level combining cohorts 1 and 2 at month 3,6,9 and 12 or early termination.

